#### **6.3.4.2. Supportive Analysis**

Time to return to normal function through 8 hours postdose distribution will be presented, separately. Kaplan-Meier plot will also be displayed (see Section 5.2.3 for details).

### **6.3.5. Percentage of participants with phonophobia absent at 15 minutes, 30 minutes, 45 minutes, 60 minutes, 90 minutes, 2 hours, 3 hours, 4 hours, 6 hours, 8 hours, 24 hours, and 48 hours postdose**

#### **6.3.5.1. Main Analysis**

- Estimand strategy: Composite policy (Section 2.2.3).
- Analysis set: EAS (Section 4). Participants with phonophobia present at the time of dosing will be included.
- Analysis methodology: The Mantel-Haenszel risk estimation stratified by country/region will be used. See details in Section 5.2.2.
- Intercurrent events and missing data: (1) Taking rescue medication at or before each of the time points postdose (RM=F; see Appendix 2.1) and (2) missing phonophobia status at each of the time points postdose respectively (NC=F; see Section 5.3 for definition) will be regarded as failures.

Treatment group comparisons of the percentage of participants with phonophobia freedom at each time point from 15 minutes through 48 hours postdose (i.e., in the 15-minute to 48 hours postdose analysis window) will present similar statistics as the main analysis of the co-primary endpoint of pain freedom (see Section 6.1.1.1).

### 6.3.5.2. Supportive Analysis

Time to phonophobia freedom through 8 hours postdose distribution will be presented. Kaplan-Meier plot will also be displayed (see Section 5.2.3 for details).

### 6.3.6. Percentage of participants with photophobia absent at 15 minutes, 30 minutes, 45 minutes, 60 minutes, 90 minutes, 2 hours, 3 hours, 4 hours, 6 hours, 8 hours, 24 hours, and 48 hours postdose

#### 6.3.6.1. Main Analysis

- Estimand strategy: Composite policy (Section 2.2.3).
- Analysis set: EAS (Section 4). Participants with photophobia present at the time of dosing will be included.
- Analysis methodology: The Mantel-Haenszel risk estimation stratified by country/region will be used. See details in Section 5.2.2.
- Intercurrent events and missing data: (1) Taking rescue medication at or before each of the time points postdose (RM=F; see Appendix 2.1) and (2) missing photophobia status at each of the time points postdose respectively (NC=F; see Section 5.3 for definition) will be regarded as failures.

Treatment group comparisons of the percentage of participants with photophobia freedom at each time point from 15 minutes through 48 hours postdose (i.e., in the 15-minute to 48 hours postdose analysis window) will present similar statistics as the main analysis of the co-primary endpoint of pain freedom (see Section 6.1.1.1).

#### 6.3.6.2. Supportive Analysis

Time to photophobia freedom through 8 hours postdose distribution will be presented. Kaplan-Meier plot will also be displayed (see Section 5.2.3 for details).

### 6.3.7. Percentage of participants with nausea absent at 15 minutes, 30 minutes, 45 minutes, 60 minutes, 90 minutes, 2 hours, 3 hours, 4 hours, 6 hours, 8 hours, 24 hours, and 48 hours postdose

#### 6.3.7.1. Main Analysis

- Estimand strategy: Composite policy (Section 2.2.3).

- Analysis set: EAS (Section 4). Participants with nausea present at the time of dosing will be included.
- Analysis methodology: The Mantel-Haenszel risk estimation stratified by country/region will be used. See details in Section 5.2.2.
- Intercurrent events and missing data: (1) Taking rescue medication at or before each of the time points postdose (RM=F; see Appendix 2.1) and (2) missing nausea status at each of the time points postdose respectively (NC=F; see Section 5.3 for definition) will be regarded as failures.

Treatment group comparisons of the percentage of participants with nausea freedom at each time point from 15 minutes through 48 hours postdose (i.e., in the 15-minute to 48 hours postdose analysis window) will present similar statistics as the main analysis of the co-primary endpoint of pain freedom (see Section 6.1.1.1).

#### 6.3.7.2. Supportive Analysis

Time to nausea freedom through 8 hours postdose distribution will be presented. Kaplan-Meier plot will also be displayed (see Section 5.2.3 for details).

#### 6.3.8. Percentage of participants with the PGIC overall status improvement at 30 minutes, 60 minutes, 2 hours, and 24 hours postdose

The overall status based on PGIC total score will be categorized into 3 categories: (1) improved (defined as very much improved, much improved, or minimally improved); (2) worse (defined as minimally worse, much worse, or very much worse); (3) no change

At each time point postdose, number and percentage of participants in above 3 categories will be tabulated by treatment group.

For the percentage of participants with the PGIC overall status improvement (above category 1), the ASE and a 95% CI based on normal approximation will be presented for each group and the Mantel-Haenszel risk estimation stratified by country/region will be used for percentage difference between treatment groups with ASE, 95% CI, and p-value presented (See Section 5.2.2). Taking rescue medication at or before each of the time points postdose will be regarded as failures (RM=F; see Appendix 2.1) and the missing PGIC overall status at each of the time points postdose respectively (NC=F; see Section 5.3 for definition) will be regarded as failures.

#### 6.4. Subset Analyses

For the co-primary and key secondary endpoints, subgroup analyses will be conducted for the following baseline demographic and characteristic variables:

- Country/region at randomization: China, Korea, Taiwan
- Age at informed consent category 1: <40, ≥ 40

- Sex: male, female
- BMI category:  $<25 \text{ kg/m}^2$ ,  $\geq 25$  to  $<30 \text{ kg/m}^2$ ,  $\geq 30 \text{ kg/m}^2$
- Aura on study before dosing: yes, no
- History of migraine with aura: yes, no (see Section 6.5.1.2)
- Historical number of moderate to severe migraine attacks per month:  $<4$ ,  $\geq 4$  (overall median)
- Stable prophylactic migraine medication use through randomization: yes, no.

For the primary endpoint of “percentage of participants with an MBS reported before dosing that is absent at 2 hours postdose”, the following characteristic variables will additionally be used for subgroup analysis:

- MBS on study before dosing: Nausea
- MBS on study before dosing: Phonophobia
- MBS on study before dosing: Photophobia

Main analysis method described in Section 5.2.2 will be used, except for the subgroup analysis by country/region at randomization, in which Mantel-Haenszel risk estimation without stratification will be conducted.

## 6.5. Baseline and Other Summaries and Analyses

### 6.5.1. Baseline Summaries

Baseline summaries will include the following: demographics and other relevant baseline characteristics, migraine history, migraine characteristic at the time of dosing, medical history, and prior non-study medications. Unless specified otherwise, baseline summaries will be presented for EAS and safety analysis set, respectively.

#### 6.5.1.1. Demographic and Baseline Characteristics

Demographics and baseline characteristics will be summarized for the variables listed in Section 3.4.

#### 6.5.1.2. Migraine History

Migraine history will include the following:

- Age (years) at migraine onset
- Time since last migraine (days)
- Number of moderate to severe migraines per month, also categorized as  $< \text{median}$ ,  $\geq \text{median}$ , where the median is calculated overall across treatment groups combined for the efficacy analysis set and rounded to an integer
- Average duration of untreated migraine attacks (hours)

- Most bothersome symptom (i.e., nausea and/or vomiting, photophobia, or phonophobia)
- Migraine symptoms (i.e., headache attacks lasting 4-72 hours, unilateral location, pulsating quality, moderate or severe pain intensity, aggravation by or causing avoidance of routine physical activity, nausea and/or vomiting during headache, photophobia and phonophobia during headache)
- History of migraine without aura (yes, no)
- History of migraine with aura (yes, no)

#### **6.5.1.3. Migraine Characteristics at the Time of Dosing**

Migraine characteristics at the time of dosing include the following parameters:

- Pain intensity (none, mild, moderate, severe)
- MBS (nausea, phonophobia, photophobia) on study before dosing
- Nausea status (present, absent)
- Nausea intensity (none, mild, moderate, severe)
- Phonophobia status (present, absent)
- Phonophobia intensity (none, mild, moderate, severe)
- Photophobia status (present, absent)
- Photophobia intensity (none, mild, moderate, severe)
- Functional disability level (normal, mildly impaired, severely impaired, requires bedrest)
- Aura (yes, no) on-study before dosing.

An intensity of none for a symptom (nausea, photophobia, or phonophobia) is defined as a symptom status of absent. See Section 5.2.5 for additional details.

#### **6.5.1.4. Medical History**

Medical history will be summarized by system organ class (SOC) and preferred term (PT), and displayed in descending order of overall frequency within SOC and PT.

A separate table summarizing the medical history of hypertension will be produced. A participant is considered to have medical history of hypertension if  $\geq 1$  medical history PTs are among the prespecified list of PTs defined in Section 6.6.1.3.

#### 6.5.1.5. Non-study Medications

The following non-study medications are tabulated by preferred name using safety analysis set:

- Prior medications: defined as those taken before study intervention starts.
- Concomitant medications: defined as those taken on or after study intervention starts. Non-study concomitant rescue medications will be additionally tabulated in a separate summary.
- Stable prophylactic migraine medications through randomization: defined as prophylactic migraine medication taken  $> 3$  months before informed consent and through randomization.

#### 6.5.2. Participant Disposition

Participant disposition will be summarized for all randomized participants (FAS) by study phase including the number and percentages of participants enrolled, treated, completed the study, discontinued from the study and the primary reason of discontinuation.

#### 6.5.3. Summary of Analysis Sets

The number and percentage of participants screened and included in each analysis set as defined in Section 4 will be summarized.

#### 6.5.4. Study Treatment Exposure

Study intervention exposure is summarized by treatment group for FAS that includes the number and percentage of participants in the following categories:

- Study intervention taken (i.e., study intervention start date/time not missing)
  - Study intervention actually received different from randomized treatment assignment
- Study intervention not taken (i.e., study intervention start date/time missing)

### 6.6. Safety Summaries and Analyses

Safety analyses are based on the safety analysis set by as-treated treatment group. Safety parameters include death, AEs, laboratory tests, vital signs, and ECGs.

## 6.6.1. Adverse Events

### 6.6.1.1. AE Overview

An AE overview without SOC and PT will present the number of participants evaluable for adverse events, the number of adverse events, the number and percentage of participants with: any AE; mild AE; moderate AE; severe AE; moderate or severe AE; SAE; AE leading to study discontinuation; hepatic-related AE; potential drug abuse AE; cardiovascular AE; suicidality AE; local irritation AE; hypertension AE; Raynaud's phenomenon AE.

An AE overview will be produced by treatment group for each analysis period as defined in Section 5.2.4 using the safety analysis set. All-cause TEAEs (for on-treatment period and follow-up period) and treatment-related TEAEs (for on-treatment period) will be generated separately.

### 6.6.1.2. AEs by SOC and PT

All-cause TEAEs (for each analysis period) and treatment-related TEAEs (for on-treatment period) will be generated separately for below summaries.

#### 6.6.1.2.1. Pre-treatment AEs

Pre-treatment AEs will not be summarized, and will be included in the AE listing.

#### 6.6.1.2.2. On-Treatment Treatment Emergent AEs (TEAE)

An AE is considered a treatment-emergent AE if the event started after the study intervention start date/time. All-cause and treatment-related TEAEs will be summarized by SOC and PT for the safety analysis set by treatment group for the following endpoints:

- TEAEs
- TEAEs by severity (total, mild, moderate, severe, not reported)
- SAEs

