### **2.2.2.3. Clinical Safety**

In clinical studies, approximately 2700 participants have been administered zavegepant IN, and approximately 606 participants have been administered oral zavegepant. Administration of zavegepant was well tolerated at 5 mg, 10 mg, and 20 mg as a single IN spray in 1185 adult participants with migraine (BHV3500-201). A similar safety profile was observed in the 629 adult participants administered a single dose of zavegepant 10 mg IN for the acute treatment of migraine (BHV3500-301).

Zavegepant 10 mg IN was well tolerated in a completed long-term safety study (up to 8 doses per month) in 603 adult participants with migraine for up to 52 weeks (BHV3500-202). The most frequently occurring adverse events in clinical studies to date have been associated primarily with intranasal administration (ie, dysgeusia, throat irritation, nasal congestion, nasal discomfort), as well as nausea and back pain, and the majority have been of mild to moderate intensity.

BHV3500-106 was a Phase 1, daily dosing, open-label, safety study of oral zavegepant 100 mg QD in healthy participants. The dose selected for this daily dosing study was based on achieving exposures of zavegepant similar to that for the 10 mg once daily dose administered by the intranasal route. In this study, oral zavegepant 100 mg once daily for up to 8 weeks in healthy participants was well tolerated and demonstrated a favorable safety profile. Through demonstration of clinically relevant sustained systemic exposure after oral administration of zavegepant, the results of this study support the safety conclusions and the overall benefit-risk assessment for the intranasal route of administration.

Refer to the IB for more details on the clinical safety of zavegepant.

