#### 5.2.4. Safety Analysis Periods

Analysis periods	Start date/time	End date/time	Usage
Pre-treatment		Study intervention start date/time	To be used to derive baseline values and to assess the safety endpoints prior to study intervention
On-treatment safety	Study intervention start date/time	Later of (1) Study intervention start date + 9 days and (2) EOT visit date	To be used to assess the safety endpoints during treatment period
Follow-up safety	Later of (1) Study intervention start date + 10 days and (2) EOT visit date + 1 day		To be used to assess the safety endpoints of the follow-up period

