### 6.6.1.3. Other Significant AEs

All-cause (for on-treatment period and follow-up period) and treatment-related (for on-treatment period) AEs will be generated separately for other significant AEs, which will be summarized by SOC and PT for the safety analysis set by treatment group:

- Hepatic-related AEs
- Cardiovascular AEs
- Suicidality AEs
- Local irritation AEs
- Potential drug abuse AEs
- Hypertension AEs
- Raynaud's phenomenon AEs

Potential drug abuse AEs will be displayed in alphabetical order by severity and PT without SOC.

Definitions of the above AEs are described in the following and [Appendix 3.1](#), and are subject to change due to sponsor internal update; minor updates to the definitions will be included in the programming A&R plan before study database lock.

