#### Potential Drug Abuse AEs

Potential drug abuse AE PTs will include any of the following:

- “Drug abuse, dependence and withdrawal” SMQ: All PTs
- PTs in [Table 3 \(Appendix 3.1\)](#). This list is based on clinical review of AE PTs in the depressant, stimulant, and psychotomimetic categories of the General disorders and administration site conditions SOC, Nervous system disorders SOC, and Psychiatric disorders SOC, as recommended in FDA Guidance for Industry Assessment of Abuse Potential of Drugs Section V.B (January 2017). Note that some PTs in this list are also part of the “Drug abuse, dependence and withdrawal” SMQ.

- PT of dizziness only if concurrent with any euphoria-related AE in [Table 4 \(Appendix 3.1\)](#), which is a subset of PTs in [Table 3 \(Appendix 3.1\)](#).
  - For a given safety analysis period, AEs are considered concurrent if (1) their durations overlap, and (2) their AE start dates are in the same safety analysis period.

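### The TEAE definition requires onset strictly after dosing, and the safety periods overlap at the dosing instant, so an AE recorded at that moment can drop out of the TEAE tables

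*SAP*

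**What the plan says.** The TEAE rule is in SAP 6.6.1.2.2: "An AE is considered a treatment-emergent AE if the event started after the study intervention start date/time". SAP 6.6.1.2.1 deals with what lies before dosing: "Pre-treatment AEs will not be summarized, and will be included in the AE listing".

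SAP 5.2.4 defines the safety analysis periods. Pre-treatment ends at the dosing date/time and on-treatment starts at the same date/time. The table does not say whether either bound is inclusive. The pre-treatment period has a second use: "To be used to derive baseline values and to assess the safety endpoints prior to study intervention".

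The AE tables do not share one basis. For the overview, SAP 6.6.1.1 says: "All-cause TEAEs (for on-treatment period and follow-up period) and treatment-related TEAEs (for on-treatment period) will be generated separately". The SOC/PT and severity tables in 6.6.1.2 are also built on TEAEs. For local irritation and the other special categories, SAP 6.6.1.3 says: "All-cause (for on-treatment period and follow-up period) and treatment-related (for on-treatment period) AEs will be generated separately for other significant AEs". That sentence names AEs by period and does not mention treatment emergence.

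SAP 3.2.2 lists moderate or severe AEs and local irritation AEs among the secondary endpoints. Protocol 2.2.2.3 links the most frequent AEs mainly to the nasal route ("ie, dysgeusia, throat irritation, nasal congestion, nasal discomfort").

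**The concern.** This is a single spray taken at home, and its known reactions are associated mainly with the act of administration. An onset recorded at the dosing time is therefore a plausible entry. A rule that needs onset strictly later than the dose excludes exactly that entry from the TEAE tables.

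Two things are at stake. First, an event at the dosing instant may be missing from the overview and from the severity tables that report moderate and severe AEs. Second, the same local irritation event may be counted in one table and not in another, which leaves the clinical study report with two figures for one secondary safety endpoint.

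A related gap concerns AEs with a start date on the dosing day but no time. Whether they count as treatment-emergent depends on a choice that the SAP does not state, so it would be made in programming.

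**Working it through.** The plan states no figure on this point, so the check is logical: classify possible onset records under the written rules.

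**Inputs.** TEAE rule: onset later than the dose (SAP 6.6.1.2.2). Pre-treatment: up to the dose; on-treatment: from the dose (SAP 5.2.4). Both bounds are read as inclusive, which is an assumption because the table is silent. The last column replaces the rule by onset at or after the dose.

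| Recorded onset | TEAE as written | Pre-treatment | On-treatment | TEAE if at or after |
|---|---|---|---|---|
| 1 minute before dose | no | yes | no | no |
| Same minute as dose | **no** | **yes** | **yes** | yes |
| 1 minute after dose | yes | no | yes | yes |
| Dosing day, no time, filled as 00:00 | no | yes | no | no |
| Dosing day, no time, filled as dose time | no | yes | yes | yes |
| Dosing day, no time, filled as 23:59 | yes | no | yes | yes |

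If dates alone are compared, a dosing-day onset is not a TEAE under the written rule and is one under at or after.

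**Same-minute onset.** The event fails the TEAE rule but lies in both periods. It is left out of any table restricted to TEAEs, yet it qualifies for the on-treatment table of 6.6.1.3. If both bounds were instead read as exclusive, the event would lie in neither period. The text does not settle which.

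**The later boundary is clean.** On-treatment ends at "Later of (1) Study intervention start date + 9 days and (2) EOT visit date". Follow-up starts at the later of day +10 and the EOT visit date + 1 day, which is always exactly one day after the on-treatment end. Only the boundary at dosing overlaps.

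**Dosing-day onset without a time.** The answer changes with the value filled in. SAP 6.6.2.2 refers to an imputed AE start date, so some imputation is intended, but no rule is printed. SAP 5.3 covers binary efficacy endpoints only. For rescue medication, SAP Appendices 2.1.1 and 2.1.2 do say what happens when the date is known and the time is missing; nothing equivalent exists for AEs. Changing the operator alone is not enough, because a fill of 00:00 still gives no TEAE.

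**Other boundaries in the SAP.** SAP 6.5.1.5 counts a medication as concomitant if taken on or after the start of study intervention. SAP 3.5.2 to 3.5.4 take the baseline value as the last one on or before dosing. The strict rule for AEs differs from the medication rule, and no reason is given.

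**Size.** Let p be the share of an arm whose only qualifying event starts at administration, and s the share of those onsets recorded so that they fail the rule. The arm loses p × s, and the difference between arms is understated by p × s for zavegepant minus p × s for placebo. Neither document gives p or s for either arm. If s is zero, nothing is lost.

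**The case against.** A reader might infer that immediate spray reactions, and all dosing-day onsets without a time, become pre-treatment AEs by rule, disappear from every table, and so dilute the safety contrast with placebo by some percentage points. The documents do not support this, for five reasons.

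- SAP 5.2.4 also starts the on-treatment period at the dosing instant. No sentence sends such an AE to pre-treatment only.
- Local irritation AEs have their own on-treatment table in 6.6.1.3, and an onset at the dosing instant may well be counted there. Any AE left out of the summaries as pre-treatment remains in the listing.
- Onsets without a time are unclassified, not classified as pre-treatment. The condition in the drug-abuse section, "their AE start dates are in the same safety analysis period", decides only whether dizziness is concurrent with a euphoria-related event. It is not a general rule for placing AEs in periods.
- No onset time is given for any reaction, and neither document says whether the CRF records an AE start time. It is also not established that these events are recalled only at the EOT visit: the schedule of activities marks AE monitoring in the dosing and postdose columns as well.
- Any figure for the understatement would rest wholly on assumed reaction rates and recording habits.

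It is also fair to say that the AE summaries are descriptive and that protocol 9.3.5 already commits to tabulating postdose events.

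All of this limits the point but does not remove it. The TEAE rule as written still excludes an onset at the dosing instant. Moderate and severe AEs across all terms have no second table outside the TEAE basis. The possible disagreement between 6.6.1.1 and 6.6.1.3 follows from the text itself.

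**Conclusion.** The point holds as a defect of definition. An AE recorded at the dosing date/time is not a TEAE, lies on an overlapping period boundary, and can be missing from the TEAE tables while a local irritation event still appears in 6.6.1.3. The classification of dosing-day onsets without a time is undefined.

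The conclusion rests on a literal reading of *after* and, for the double count, on inclusive period bounds. It does not rest on any assumed reaction rate. The size cannot be estimated from the documents and may be nil. The efficacy analyses are not affected. The change is worth making because it concerns secondary safety endpoints of a nasal product, costs very little, and is best settled before unblinding.

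**What to change.** Four short changes to the SAP:

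1. In 6.6.1.2.2, define a TEAE as an AE that started at or after the study intervention start date/time.
2. In 5.2.4, add that an AE starting at the dosing instant belongs to the on-treatment period only. Limit this to AE assignment, because the pre-treatment period is also used to derive baseline; the on-or-before baseline rule in 3.5.2 to 3.5.4 stays unchanged.
3. State that an AE with onset on the dosing date and a missing time is treatment-emergent unless it is recorded as starting before dosing. This rule is needed in addition to change 1.
4. In 6.6.1.3, state that the tables use the same TEAE definition as 6.6.1.1 and 6.6.1.2.

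The cost is a few sentences and a small change to the AE derivation, with no new data collection. The downside is that TEAE counts may rise slightly, and a dosing-day event that in fact began before the dose, but was not recorded as such, would be counted as treatment-emergent.
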